The proposed 6-mo. pilot trial will compare the feasibility and effectiveness of DPP delivered through Facebook (DPP-FB) or group format delivered remotely by phone conference call (DPP-R) in 30 adults (age ≥ 18 yrs.) with prediabetes. Both interventions will be delivered through the CES, which serves as the community outreach arm of all land grant universities through over 2,900 offices across the U.S. The Kansas State Research and Extension (KSRE) (Kansas version of CES), is well positioned, but underutilized for the delivery of DPP in rural areas. Delivery of DPP by a well-recognized entity, such as the KSRE, may improve the probability of dissemination and long-term program sustainability. Two CES offices serving rural counties in Kansas will be randomized (1:1) to the DPP-FB or DPP-R arms. Our research team will train 2 professional staff from KSRE (with backgrounds in nutrition programming and family consumer science) who will deliver the DPP intervention. Outcomes will include body weight

and moderate-vigorous physical activity assessed at baseline, 3 mos. and 6 mos., participant retention, i.e. weight assessed at 6 mos., program attendance (percentage of 16 sessions attended), and the fidelity of intervention delivery. i.e., the delivery of $\geq 80\%$ of scheduled content as determined by reviewing audio recordings of all DPP sessions. This project will address the following aims:

Primary aim: **Compare weight and MVPA between DPP-FB and DPP-R across 6 mos.** We expect greater weight loss and MVPA in the DPP-R arm compared with the DPP-FB arm.

Secondary aim: **Compare the feasibility of DPP-FB and DPP-R across 6 mos. based on participant retention and program attendance.** We expect greater participant retention and program attendance in the DPP-R arm compared with the DPP-FB arm.

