Reimbursement of DPP. The CDC maintains a registry of community organizations that have satisfied requirements for delivery of the DPP program. The CDC recognizes multiple delivery options for the DPP including: in-person, online, distance learning and a combination program. Recognized programs are eligible for cost reimbursement from the Centers for Medicare and Medicaid Services (CMMS); however, only in-person programs are currently eligible for reimbursement. Additional research to evaluate the feasibility and effectiveness of alternative delivery methods such as group video conferencing and Facebook, as we have proposed, will contribute to the knowledge base required to obtain CMMS reimbursement in the future.

INNOVATION

Innovative aspects of this proposal include: 1) Targeting an under-served, at-risk group, i.e., rural residents at risk for T2D, 2) Partnering with Kansas State Research and Extension (KSRE) that is an established and a widely utilized community outreach arm across the state of Kansas, 3) Using existing KSRE infrastructure for intervention delivery in rural communities which may increase the probability of perpetuation and reach of the intervention.

APPROACH

Design overview. The proposed 2-arm trial will compare the feasibility and effectiveness of Facebook or remote-delivery of the DPP in rural adults with prediabetes both delivered through the KSRE. The CES is a non-formal educational program, implemented in the U.S. through each state's designated land grant university, to help people use research-based knowledge to

improve their lives. The KSRE maintains local units which are comprised of single counties or multi-county districts. Two KSRE local units serving rural counties will be identified by our partners at KSRE and randomized to the Facebook or remote delivery arms. Members of the KUMC research team will recruit and consent participants and will train KSRE personnel to deliver the 30 core-sessions of the DPP protocol over 12 mos. Outcomes will be assessed by the research team at the local CES offices at baseline, 3 mos. 6 mos. and 12 mos.

Meets At-Risk Qualification:		
Complete the questions below based on the candidate's responses.		
	Yes - Points	No - Points
Is the candidate a woman who has had a baby weighing more than 9 pounds at birth?	 - 1	 - 0
Does the candidate have a parent with diabetes?	 - 1	 - 0

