Does the candidate have a brother or sister with diabetes?	 - 1	 - 0
Does the candidate weigh as much as or more than the weight listed for their height?	 - 5	 - 0
Is the candidate younger than 65 years of age and gets little or no activity in a typical day?	 - 5	 - 0
Is the candidate between 45 and 64 years of age?	 - 5	 - 0
Is the candidate 65 years of age or older?	 - 9	 - 0
Total Risk Score (score must be 9 or greater to qualify for enrollment in 'At-Risk' category):		

Participants/Recruitment: Men and women (n=15 per arm) who satisfy the inclusion/exclusion will be recruited through local physician's offices, social media, KSRE offices, marketing/listservs, and local businesses. Interested potential participants will fill out an initial eligibility questionnaire via website or over the phone with a study team member. If they pass the screening, a consent session will be scheduled over the phone or over Zoom. The consent form will be emailed to participants prior to the consent session so ensure understanding of the study. The participant will have the option to sign the consent form and email it to the study coordinator or sign the consent form in REDCap.

Inclusion/exclusion criteria. *Inclusion:* 1) Prediabetes as defined as A1C = 5.7-6.4%, fasting glucose = 100-125 mg/dl, (confirmed from physician/medical record in the previous year), history of gestation diabetes mellitus OR a positive result based on the CDC- DPP screener (see figure), 2) Age ≥ 18 yrs., 3) Willing to commit to participate on a weekly basis for the 6 month intervention, 4) Living in the county of a rural KSRE local unit. Rural counties will be defined using the American Community Survey definition which categorizes a county as rural if the population is $< 65,000$ (23), 5) Internet access and capability to use Zoom, 6) Clearance from primary care physician and 7) Access to a scale. *Exclusion.* 1) Diagnosis of T2D, 2) Unable to participate in physical activity.

Randomization: Two rural KSRE local units will be randomized in a 1:1 ratio to either DPP-FB or DPP-R.

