Intervention overview: The DPP is an evidenced based lifestyle intervention based on Social Cognitive Theory which includes topics on nutrition and physical activity in addition to behavior change strategies such as self-monitoring, environmental control, positive reinforcement and accountability (24). Six-month weight loss and physical activity goals, i.e. following completion of the 24-session core curriculum, are 5%-7% and ≥ 150 min/wk. of moderate intensity activity such as brisk walking, respectively. The nutrition portion of the DPP curriculum focuses on reducing fat intake to reduce caloric intake. The physical activity portion of the curriculum focuses on incorporating physical activity throughout the day to reach the goal of 150 min/wk. Increasing lifestyle activities such as taking the stairs, stretching, gardening, and parking further away at the grocery store, etc. are encouraged. At the baseline visit, participants in both

intervention arms will receive a notebook which includes contact information for study personnel, instructions and guidelines for phone calls (DPP-R only), descriptions of the diet and physical activity protocols, handouts/worksheets/assignments specific to each meeting, and charts to self-monitor, weight, physical activity, and fruits and vegetables consumption.

DPP-R intervention delivery. Weekly 60 min. group meetings (12-15 participants) will be held by Zoom over 6 months followed by monthly 60 min. group meetings for the later 6 months. Approximately 5 min prior to the meeting time (typically early evening) participants will receive call in information to join the group meeting by video conferencing or phone.

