shown to provide valid and reliable assessments of PA in adults. Participants will wear the ActiGraph on a belt over the non-dominant hip at the anterior axillary line during waking hours for 7 consecutive days, except for bathing, swimming, and contact sports. A 7-day monitoring period provides a reliable estimate of moderate-to-vigorous PA. ActiGraph data, aggregated over 1-min epochs, will be processed using the protocol used for adults in the 2003-2004 and 2005-2006 cycles of NHANES using the following intensity cut-points: sedentary (< 1.0 METs \leq 100 counts/min), light (METs 1.1-2.99; 101-2019 counts/min.), moderate (METs 3.0-5.99; 2020-5998 counts/min) and vigorous (\geq 6 METs; \geq 5999 counts/min). ActiGraphs will be given to participants during outcomes testing with a prepaid envelope to mail back to the investigators after wearing for 7 days. Participant retention/program attendance. Lifestyle coaches in both intervention arms will maintain records of participant retention and program attendance. Retention will be defined as attendance at 6 mo. and 12 mo. outcome testing. Program attendance will be defined as being present as the beginning and end of the class/call and reporting weekly data.

End study survey. At the end of the 6 mo. intervention, a survey will be conducted to ask about your experience with the program.

Focus group. At the end of the 6 mo. intervention, a recorded focus group will be conducted in all participants to gather information on the overall ease and enjoyment of the program. Questions on barriers to healthy eating and physical activity, time commitment, recommending the program to friends/family,

Statistical analysis & Data management: Baseline measures and demographic characteristics will be summarized for the complete sample using means and standard deviations for continuous variables and frequencies and percentages for categorical variables. Weight loss will be calculated as the difference in body weight between baseline and 6 months. All analyses will be conducted using SAS 9.4 (SAS Institute, Cary, NC). We will compare change in body weight and MVPA between groups at 6 mos. and 12 mos. by using a two-sample t-test. Feasibility will be calculated as the percentage of participants who attended $>$ 75% of the scheduled sessions. We will also conduct a qualitative analysis of focus group and end study surveys to gain insight on the acceptability and enjoyment of the program and suggestions for improvement.

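### Does comparing MVPA only by an unadjusted t-test on change, with one local unit per arm, leave a fault in the analysis?

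*Combined protocol and SAP*

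**What the plan says.** The primary aim (Specific aims) is to compare weight and MVPA between the Facebook arm (DPP-FB) and the remote arm (DPP-R) across 6 months, with the hypothesis "We expect greater weight loss and MVPA in the DPP-R arm compared with the DPP-FB arm".

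Under Randomization: "Two rural KSRE local units will be randomized in a 1:1 ratio to either DPP-FB or DPP-R". Each arm is therefore one local unit. Participants/Recruitment gives 15 people per arm.

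The section Statistical analysis & Data management holds the whole analysis plan:

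- Baseline: "Baseline measures and demographic characteristics will be summarized for the complete sample".
- Definition of change, given for weight only: "Weight loss will be calculated as the difference in body weight between baseline and 6 months".
- Comparison: "We will compare change in body weight and MVPA between groups at 6 mos. and 12 mos. by using a two-sample t-test".

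No covariate, adjusted model or sensitivity analysis is named. The documents give no alpha, power, effect size, MVPA standard deviation, baseline-to-follow-up correlation or intraclass correlation. The end of Specific aims describes the study as a source of pilot data for a later, adequately powered trial.

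**The concern.** Subtracting baseline fixes the slope of follow-up on baseline at 1. Accelerometer MVPA may well have a slope below 1, so people who start high tend to fall back and people who start low tend to rise. If the two arms start apart by chance, part of the gap closes without any intervention effect, and the change score counts that as a difference between arms.

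The design makes a starting gap plausible. There are 15 people per arm, individuals are not randomized, and each arm comes from one place. Since the plan commits only to a pooled baseline summary, a reader might see neither the gap nor its influence. Figures for planning a larger trial could then rest on an imbalance nobody had seen.

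There is also a point of wording. Change is defined for weight only, and the hypothesis could be read as greater weight loss and a greater level of MVPA. A comparison of levels would fix the slope at 0.

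**Working it through.** **Inputs.** From the documents: n = 15 per arm, two arms (2 x 15 = 30, which agrees with the stated total), one local unit per arm, a two-sample t-test on change. Assumed, because the documents give no figure: correlation r between baseline and follow-up MVPA, ratio k of follow-up SD to baseline SD, and the size of any gap. Results are in baseline SD units. The plan states no derived figure to reproduce.

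**1. How far apart the two estimates can be.** With D the baseline gap and b the fitted within-arm slope,

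adjusted estimate - change estimate = (1 - b)D.

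This identity is exact in the same participants. In expectation b = rk. A one-standard-error chance gap is D = sqrt(2/15) = 0.365.

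| k | r | (1 - rk) x 0.365 |
|---|---|---|
| 1 | 0.5 | 0.183 |
| 1 | 0.7 | 0.110 |
| 1.25 | 0.5 | 0.137 |
| 1.25 | 0.8 | 0.000 |
| 1.5 | 0.7 | -0.018 |

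Over the assumed range the distance passes through zero and changes sign. At r = 0.5, k = 1 the change-score 95% CI half-width is t28 x sqrt((2/15) x 2(1 - r)) = 2.048 x 0.365 = 0.748, so 0.183 is about a quarter of it.

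**2. Is the planned test wrong when the gap is chance?** Take k = 1. Given the realised D, the change score is off by (1 - r)D in size. Over repeated samples D averages zero, so the average error is zero. The extra spread is already in the test's standard error:

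(2/15)(1 - r^2) + (1 - r)^2(2/15) = (2/15) x 2(1 - r).

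At r = 0.5 this is (2/15)(0.75 + 0.25) = (2/15)(1.0). The left side is residual variation plus variation from chance gaps; the right side is the variance the change-score t-test uses. Simulation agrees: with no unit effect, mean error is 0.00 and coverage about 0.95 at r = 0.5 and r = 0.7.

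**3. Is it wrong when the units differ stably?** If one unit is higher by g at both visits, g cancels in the change score: bias 0.00, coverage 0.95. The adjusted model removes only rg (k = 1) and keeps (1 - r)g as bias.

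| Stable gap g (r = 0.5, k = 1) | Adjusted bias | Adjusted coverage | Change coverage |
|---|---|---|---|
| 0.365 | 0.18 | 0.919 | 0.95 |
| 0.5 | 0.25 | 0.890 | 0.95 |
| 1.0 | 0.50 | 0.732 | 0.95 |

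The 1 SD row is an extreme: by chance alone P(|D| > 1) = 2(1 - Phi(1/0.365)), about 0.6%.

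**4. Would the second model gain precision or settle the cause?** The ratio of adjusted to change CI half-width depends on the assumptions: 0.884 at k = 1, r = 0.5; 0.965 at k = 1.25, r = 0.5; 1.002 at k = 1.5, r = 0.5; 1.020 at k = 1.5, r = 0.7. No general gain follows.

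With 30 people the slope is itself loose. At r = 0.5, k = 1 its 95% range is about 0.16 to 0.84, so for D = 0.365 the reported divergence could lie between (1 - 0.84) x 0.365 = 0.06 and (1 - 0.16) x 0.365 = 0.31. The size of that divergence does not show whether the gap was chance or stable.

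**5. Unit effects.** If the units shift differently between visits, both intervals under-cover. With an assumed intraclass correlation of 0.05 at follow-up, coverage is about 86% for change and 84% for adjusted (r = 0.5, k = 1). That comes from having one unit per arm, and baseline adjustment does not repair it.

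**6. Wording.** In the comparison sentence the word change governs both outcomes. The definition given for weight supplements that sentence and does not turn MVPA into a comparison of levels.

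**The case for a change.** The strongest opposing case is conditional. The trial will have one realised gap, and a reader cares about error given that gap. If the gap is chance and regresses, then at r = 0.5 and k = 1 the nominal 5% change-score test rejects about 7% of the time given a 0.5 SD gap and 25% given a 1 SD gap. A gap above 0.5 SD arises by chance in 17% of trials of this size, and in 20% to 38% at assumed intraclass correlations of 0.01 to 0.10. A planner would want to see the gap, and fixing a second model in advance prevents a choice between estimates after the data are in.

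The arithmetic stands. But those rates hold only given the gap, and they are offset by a rate of about 2.4% when the gap is zero at the same r. They also assume that the adjusted model is true, which allocation of two intact units does not secure. If the units differ stably, the adjusted result is the misleading one.

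What remains is that baseline MVPA by arm would help a reader. With that table and the change result, the estimate at any assumed slope follows by simple arithmetic without a second model. A pooled summary in a brief plan does not rule out by-arm columns.

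**Conclusion.** The concern does not hold. For two non-equivalent intact groups, change scores and baseline adjustment rest on different assumptions, and neither dominates. The planned t-test is unbiased on average with about 95% coverage under a chance gap and under a stable unit difference, provided unit effects do not shift between visits. The adjusted model fails the stable case, with coverage falling from about 92% to 73% as the gap grows from 0.37 to 1 SD (r = 0.5, equal SDs).

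The distance between the two estimates for a one-standard-error gap runs from 0.18 SD through zero to -0.02 SD in the cases shown. All of these rest on assumed correlations and SD ratios.

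The plain reading of the analysis sentence is already change for both outcomes. By-arm baseline columns are ordinary reporting that changes no planned result, and a second model is a matter of preference in a 30-person pilot with no power claim. The confounding of arm with local unit is a real limit of the design, but it is a separate matter that neither analysis resolves.
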